1.3 PROPOSED SOLUTION AND EXPECTED CONTRIBUTION

The proposed solution involves evaluating the efficacy of a personalized concurrent exercise prescription guide, specifically designed to suit the cardiovascular risk and physical capacity levels of adult CHP users. This tool aims to provide a protocol of aerobic and strength exercises, which when performed systematically, will improve the cardiovascular health and physical capacity of users.

Based on current protocols and models for exercise prescription in CRF control, the guide will implement a concurrent exercise protocol. This approach, including aerobic exercises (such as walking or jogging) and strength exercises using body weight, will be applied to a selected sample of the CHP population at CESFAM Externo. Its main advantage lies in minimizing resource use, and it has been proven to induce positive changes in CRF control and physical capacity improvement.

Action Plan:

1. Evaluation of cardiovascular risk factors and physical capacity in volunteer users.
2. Written prescription of a personalized concurrent exercise protocol, adapted to cardiovascular risk and physical capacity levels of each user.
3. Biweekly follow-up via phone calls to assess adherence to the protocol.
4. Reevaluation of cardiovascular risk factors and physical capacity.

The absence of this project would mean that CHP users would not have access to an essential tool for improving cardiovascular health and physical capacity, perpetuating current compensation levels, which are approximately 54%. Moreover, without this project, a crucial opportunity to align with the National Health Strategy for 2030 would be lost. This strategy not only advocates for lifestyle improvements and reduction of non-communicable chronic diseases but also emphasizes empowering individuals in managing their own health. Additionally, it underscores the need to implement evidence-based actions that enhance quality and safety in healthcare.

2. SCIENTIFIC COMPONENT, METHODOLOGY, ETHICS, AND PLANNING

2.1 RESEARCH QUESTION AND HYPOTHESIS

Research Question: What is the efficacy of a personalized concurrent exercise prescription guide combined with pharmacological treatment, compared to pharmacological treatment alone, in controlling cardiovascular risk factors and physical capacity in adult users of the Cardiovascular Health Program at CESFAM Externo de Valdivia during 2024?

Hypothesis:

- **H1:** The efficacy of a personalized concurrent exercise prescription guide combined with pharmacological treatment is greater than pharmacological treatment alone in controlling CRF and physical capacity in adult users of the Cardiovascular Health Program at CESFAM Externo de Valdivia during 2024. (hypothesis of group difference)
- **H0:** The efficacy of a personalized concurrent exercise prescription guide combined with pharmacological treatment is equal to pharmacological treatment alone in controlling CRF and physical capacity in adult users of the Cardiovascular Health Program at CESFAM Externo de Valdivia during 2024. (hypothesis of group difference)

Statistical Hypothesis:

- **Group Difference Hypothesis:**
 - **H0:** $\mu_A = \mu_B$
 - **H1:** $\mu_A > \mu_B$

2.2 OBJECTIVES

2.2.1 GENERAL OBJECTIVE Determine the efficacy of a personalized concurrent exercise prescription guide combined with pharmacological treatment, compared to pharmacological treatment alone, in controlling cardiovascular risk factors and physical capacity in adult users of the Cardiovascular Health Program at CESFAM Externo de Valdivia during 2024.

2.2.2 SPECIFIC OBJECTIVES

- Describe the effects of applying a personalized concurrent exercise prescription guide on cardiovascular risk factors in adult users of the Cardiovascular Health Program at CESFAM Externo de Valdivia.

- Describe the effects of applying a personalized concurrent exercise prescription guide on physical capacity in adult users of the Cardiovascular Health Program at CESFAM Externo de Valdivia.
- Evaluate adherence to the personalized concurrent exercise guide and pharmacological treatment in adult users of the Cardiovascular Health Program at CESFAM Externo de Valdivia.
- Describe the clinical significance of interventions through effect size calculation and perceived clinical relevance by participants regarding the interventions.

2.3 METHODOLOGY AND PROCEDURES

Research Design: The research design corresponds to a Pilot Randomized Controlled Trial (RCT), with parallel groups and superiority. The design aligns with the general objective and proposed hypothesis as it will evaluate the efficacy of a personalized concurrent exercise prescription guide combined with pharmacological treatment, compared to pharmacological treatment alone, in controlling cardiovascular risk factors and physical capacity.

Study Variables: Primary variables include the standard CHP control parameters: blood pressure, fasting glucose, total cholesterol, and triglycerides. Secondary variables include sociodemographic and medical background, physical activity level, muscular strength, cardiorespiratory capacity, body composition, adherence to the exercise guide, and patient perception of changes due to the intervention.

Population: The population will consist of adult users of the CHP registered at CESFAM Externo de Valdivia. The research team will invite users directly during their regular controls at CESFAM Externo. The research team, identified as staff from Universidad San Sebastián, will provide detailed information about the study, the exercise prescription guide, program duration, benefits, and risks in a designated space. Interested individuals will be asked to sign an informed consent form. The recruitment period will be necessary to obtain the total sample, with a maximum of 1 month. If the sample is not obtained within this period, recruitment will be extended by 1 month.

Selection Criteria: Inclusion:

- Physically inactive (not engaging in 300 or 150 min. of moderate or vigorous physical activity per week, respectively, measured with the IPAQ questionnaire)
- Body mass index (BMI) between 25 and 39.9 kg/m²
- Registered in the Cardiovascular Health Program

- Diagnosis of Hypertension with the use of 1 and/or 2 antihypertensive medications
- Diagnosis of Type 2 Diabetes Mellitus with the use of 1 oral hypoglycemic, non-insulin-dependent
- Diagnosis of Dyslipidemia with the use of 1 lipid-lowering medication
- Having a phone device

Exclusion:

- Bone disease
- Ischemic disease or arrhythmia
- Chronic respiratory disease
- Uncontrolled chronic diseases
- Inability to provide informed consent or comply with tests and exercise protocol for any reason
- History of oncological disease or undergoing investigation for suspected neoplastic disease
- Female participants who are pregnant

Sample Size Calculation: The sample size calculation will be based on literature recommendations for pilot studies and includes:

1. T-test – Means: difference between two independent means
2. Type I error: 5%
3. Statistical power: 80%
4. Effect size (ES): 0.5 according to Cohen's classification. Using these parameters, the recommended total sample size is 15 subjects per group. Assuming a 30% dropout rate, the total population will be 39 participants. After the eligibility process, participants will be randomly assigned to an experimental group (EG) and a control group (CG) using a 1:1 ratio online system (<https://www.randomizer.org/>). Assignment concealment will be carried out by an investigator not involved in the clinical procedures of the RCT using opaque, sealed, and consecutively numbered envelopes. The random sequence and assignment concealment will control selection bias.

The experimental group will receive the intervention based on the personalized exercise prescription guide plus their usual pharmacological treatment associated with the CHP, and the control group will maintain their usual pharmacological treatment associated with the CHP.

Data Collection Techniques: All evaluations will be conducted pre- and post-intervention in the experimental and control groups.

Clinical Record Information Review: The CHP medical manager, with authorization from the CESFAM Externo management and approval from the Ethics Committee of the Valdivia Health Service, will review the clinical records of participants, gathering the following information:

- Sociodemographic and medical background: sex, age, education level, duration in the cardiovascular health program, comorbidities, medications, dosage, and duration of medication use. These variables will be used to characterize the study sample.

Cardiovascular Risk Factor Evaluation: Evaluations and user follow-up will be conducted by physical therapists trained in evaluation techniques, exercise prescription, and cardiovascular risk factors, at the Universidad San Sebastián Health Center located at [name], Valdivia. A physical therapist will measure variables and be blinded to the participant's intervention assignment.

Cardiovascular Variables Evaluation: Blood pressure (systolic and diastolic) and heart rate will be measured using an automatic monitor (Omron HEM 7130™) following the standard procedure in a seated position after 15 minutes of rest, conducted before and after the intervention.

Metabolic Variables Evaluation: Blood Glucose: Blood glucose will be measured after a 12-hour fasting period using the Accu-Chek Instant device, developed by Roche Diabetes Care. This device is known for its speed and accuracy in measurements, offering results in less than four seconds and storing up to 720 results. Accu-Chek Instant complies with international standards ISO 15197:2013/EN ISO 15197:2015, ensuring reliability and precision. This device has been validated for clinical use.

Triglycerides and Cholesterol: Triglycerides and cholesterol levels will be measured using the Accutrend® Plus device (Roche, Belgium), which employs an advanced reflectance photometry method. The device's parameters for analysis are:

- Cholesterol measurement range: 150 to 300 mg/dl, with a measurement time of 180 seconds and a required sample volume of 15 to 40 µl.

- Triglycerides measurement range: 70 to 600 mg/dl, with a measurement time of 174 seconds and a required sample volume of 10 to 40 μ l. The Accutrend® Plus device has been validated for clinical use.

Health-Related Physical Capacity Evaluation: Physical Activity Level: The International Physical Activity Questionnaire (IPAQ) will be used to estimate the physical activity level before the intervention.

Isometric Muscle Strength: Handgrip Dynamometry: Handgrip strength will be assessed using a CAMRY dynamometer (CAMRY EH101), following the Southampton protocol. The procedure involves the subject sitting with their forearms supported on the chair, wrist at the edge of the armrest, in a neutral position with the thumb up, and feet on the ground. The subject is asked to squeeze the dynamometer as hard as possible for as long as possible. Three attempts are made with each hand, and the best attempt out of six is recorded.

Cardiorespiratory Capacity: Two-Minute Step Test: Preparation: Before starting the test, the height the participant's knee needs to rise will be measured by running a string from the iliac crest to the midpoint of the patella, doubling the string and marking a point on the thigh indicating the knee height for the march. The height of the step will be transferred to the wall for the participant to reference.

Procedure:

- At the signal "go," the participant begins marching in place as many times as possible for 2 minutes.
- Both knees should reach the indicated height, counting the number of times the right knee reaches the set height.
- If the participant does not reach the mark, they will be asked to reduce the pace for a valid test without stopping the time.

Scoring: The score will be the total number of complete steps in 2 minutes, counted as the number of times the right knee reaches the set height. Only one attempt will be made on the test day.

Safety norms: Participants with balance issues should be near a wall or chair for support in case of balance loss. The examiner will supervise all participants for signs of excessive exertion. After the test, participants will walk slowly for one minute.

The equation to estimate peak oxygen consumption is: $VO_2 (\text{mLkg}^{-1}\text{min}^{-1}) = 13.341 + 0.138 * \text{total steps} - (0.183 * \text{BMI})$.

Body Composition: Height will be measured with a precision stadiometer (Seca Bodymeter 206), and weight, fat mass percentage, and lean mass percentage will be measured using a bioimpedance meter (TANITA BC-534). BMI will be estimated using the formula kg/m².

Treatment Adherence: Adherence to the treatment refers to the degree to which participants follow the prescribed physical exercise guide. This variable will be operationalized as compliance with at least 70% of the scheduled exercise sessions.

Measurement Method: Adherence will be measured using two primary mechanisms:

1. **Biweekly Phone Calls:** A follow-up protocol will be established, with calls made every two weeks to participants to gather self-reported compliance data with exercise sessions. These interactions will also identify potential barriers or facilitators of adherence, allowing proactive adjustments to the intervention if necessary.
2. **Exercise Logbooks Review:** Each participant will maintain a detailed logbook of exercise sessions performed, including date, duration, and type of exercise. Reviewing these records will provide an objective measure of adherence, complementing the data obtained through phone calls.

Adherence Criteria: A participant will be considered "adherent" if they comply with at least 70% of the scheduled exercise sessions, calculated by dividing the number of completed sessions by the total number of scheduled sessions and multiplying the result by 100.

Global Rating Scale: The Global Rating Scale (GRS) will be applied as an essential instrument for evaluating the patient's perception of changes experienced in their health status, functionality, or symptoms. This evaluation will be conducted mainly at two key points: before and after the proposed clinical intervention.

The GRS methodology involves asking patients to provide a rating of their current health status compared to an established reference point, which, in our case, will be the study's start. This comparison will allow a quantitative and qualitative appreciation of the changes perceived by the patient.

To ensure a precise and adaptable evaluation, the GRS will be presented in two formats:

1. **Numerical:** Offering a range that can vary, for example, from -7 (much worse) to +7 (much better), allowing a gradable assessment of changes.

2. Descriptive: Providing qualitative terms such as "much worse," "no change," or "much better," facilitating patients' expression of change perception in a more narrative manner.

The GRS implementation will not only contribute to evaluating the intervention's effectiveness from the patient's perspective but also offer a valuable indicator of the clinical impact of the treatment. This patient-centered approach is fundamental for a comprehensive understanding of treatment outcomes, enabling adjustments and improvements in therapeutic strategies based on patient experiences and feedback.

Intervention

Experimental Group: Application of the exercise guide plus pharmacological treatment.

Exercise Guide Application: Cardiovascular Risk Classification for Exercise: Cardiovascular risk and physical capacity levels will be assessed using previously described procedures to provide a written personalized exercise protocol.

Exercise Protocol: According to the recommendations for exercise prescription for people with cardiovascular risk factors published by MINSAL, a protocol will be applied as follows:

- Protocol duration: 6 weeks.
- Frequency: 3 to 5 times per week.
- Exercise type: Concurrent, combining aerobic and muscular resistance exercises within the same program.

Aerobic Exercise: Participants will perform 5-10 intervals/session of walking or jogging at moderate to high intensity, with a rating of 5 to 8 points on the modified Borg scale (1-10 points). Each interval will consist of 1 minute of walking or jogging, followed by 2 minutes of inactive rest. Every 2 weeks, the load (cadence) will be adjusted due to normal physiological adaptations, always exercising at an intensity of 5-8 points on the modified Borg scale, similar to previous studies.

Muscular Resistance Exercise: Participants will perform concentric, eccentric, and/or isometric contractions for 1 minute at an intensity of 5-10 according to the OMNI-RES scale. The rest period will last 2 minutes, and each exercise will be repeated 3 times. Three exercises will be performed per session: squats, push-ups, and planks. Exercise difficulty (load) will be adjusted according to the user's abilities. The exercise load may be modified every two weeks according to the physiological adaptations of

the subjects, to adjust the loads to the new thresholds, always working at an intensity of 5-10 on the OMNI-RES scale.

Pharmacological Treatment: Participants will be asked to maintain their lifestyle, including taking prescribed medications as usual.

Participants will be asked to complete a "control diary" with the sessions and exercises performed during the intervention, noting any medication changes, illnesses, and additional physical activity.

Control Group: Pharmacological treatment.

Participants in the control group will be asked to maintain their current lifestyle and exercise habits throughout the study, including taking prescribed medications as usual. They will complete a "control diary" to note any exercise, medication changes, illnesses, and relevant information. Once control participants complete post-intervention evaluations, they will be offered the opportunity to complete the same intervention as the exercise group.

Statistical Analysis: In this study, dependent variables will be described using mean and standard deviation. Normality and homoscedasticity assumptions will be verified using the Shapiro-Wilk test for all data.

To identify group differences at baseline and post-intervention, the Student's t-test for independent samples will be used, complemented by Levene's test for variance comparison between groups.

A two-way repeated measures ANOVA will be used to determine intra-group and inter-group differences. Model effects will include Group (CG and EG), Time (Pre-test, Post-test), and their interaction over time (Group x Time). Tukey's post hoc test will be used for variables with Group \times Time interaction. Data analysis will be conducted by an investigator blinded to the intervention groups. Intention-to-treat analysis will be considered using the multiple imputation method for handling missing data and incomplete datasets.

The clinical significance of the interventions will be determined by effect size using Cohen's "d" (<0.2 =negligible, $0.2-0.49$ =small, $0.5-0.79$ =moderate, ≥ 0.8 =large). The clinical relevance of interventions will be assessed based on perceived therapeutic changes by participants using the Global Rating Scale (GRS). The GRS will evaluate the intervention's impact on relevant domains from the user's perspective and experience, using a 15-point Likert scale (-7=much worse, 0=no change, +7=much better). Differences interpretation: 1-3 points=small, 4-5=moderate, 6-7=significant.

All statistical analyses will be conducted using SPSS version 26 (SPSS™ Inc., Chicago, IL, USA).

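### The listed parameters (independent t-test, 5% alpha, 80% power, d = 0.5) require 64 per group two-sided or 51 one-sided, not 15; at 15 per group the power is 26% to 38%.

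*Combined protocol and SAP*

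**What the plan says.** Section 2.3, Research Design, describes a "Pilot Randomized Controlled Trial (RCT), with parallel groups and superiority" that is to evaluate efficacy. Section 2.1 states a formal null and alternative hypothesis about the group difference, with the alternative written in one direction.

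The Sample Size Calculation paragraph of section 2.3 opens: "The sample size calculation will be based on literature recommendations for pilot studies and includes". It then lists four items: a t-test for the "difference between two independent means", a 5% type I error, 80% power, and "Effect size (ES): 0.5 according to Cohen's classification". It concludes: "Using these parameters, the recommended total sample size is 15 subjects per group". A 30% dropout allowance raises the total to 39, randomised 1:1. Sidedness is not given there.

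The Statistical Analysis text of section 2.3 plans an independent-samples t-test between groups at baseline and after the intervention, and a repeated measures ANOVA with a Group x Time interaction.

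**The concern.** The paragraph claims that 15 follows from the four listed inputs. Anyone familiar with two-sample calculations will expect a figure in the fifties or sixties per group for a moderate effect at 80% power, so 15 is out by a factor of three to four.

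The consequence is a stated power that the trial does not have. If the true effect is the planned d = 0.5, a non-significant result on any one primary variable is more likely than not. A reader who trusts the 80% would take that result as evidence against the exercise guide. Conversely, a significant result requires an observed effect well above the planned one, so a positive finding would tend to overstate the benefit. That matters here because section 2.2.2 and the Statistical Analysis text use Cohen's d to describe clinical significance.

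**Working it through.** **Inputs.** From section 2.3, Sample Size Calculation: two independent means, alpha = 0.05, power = 0.80, d = 0.5 (so SD = 1), 1:1 allocation, n = 15 per group, 30% dropout, 39 in total. Sidedness is not stated there, so both cases are shown.

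**1. Attempt to reproduce 15 per group.** The normal approximation is n per group = 2(z_alpha + z_beta)² / d².

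- Two-sided: 2 × (1.960 + 0.842)² / 0.25 = 62.8, so 63.
- One-sided: 2 × (1.645 + 0.842)² / 0.25 = 49.5, so 50.

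The exact noncentral t calculation gives 63.8, so **64** (two-sided), and 50.2, so **51** (one-sided). The stated 15 is not reproduced. Other readings also fail:

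| Reading | Two-sided n | One-sided n |
|---|---|---|
| Paired or one-sample test, d = 0.5 | 34 | 27 |
| Two independent means, d = 0.8 (per group) | 26 | 21 |

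**2. Power at 15 per group.** With df = 28, the noncentrality is d × √(n/2) = 0.5 × √7.5 = 1.369. The critical t is 2.048 two-sided and 1.701 one-sided. The resulting power is **26.2%** two-sided and **37.9%** one-sided.

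**3. Effect detectable with 80% power at 15 per group.** d = **1.06** two-sided and **0.93** one-sided. Relative to the planned 0.5 these are ratios of 2.1 and 1.9.

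**4. Smallest observed effect that reaches significance at 15 per group.** Critical t × √(2/15): 2.048 × 0.365 = 0.75 two-sided; 1.701 × 0.365 = 0.62 one-sided. Both exceed 0.5.

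**5. Range over the number analysed.**

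| Analysed | Two-sided power | One-sided power |
|---|---|---|
| 14 and 13 (39 × 0.7 = 27.3 completers) | 24% | 35% |
| 15 and 15 | 26% | 38% |
| All 39, as if fully observed | 33% | 46% |

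**6. Does the repeated measures analysis rescue 15?** With two time points, the Group x Time test is a comparison of change scores, whose variance is 2(1 − r) for pre-post correlation r. To have 80% power at 15 per group, 0.5 / √(2(1 − r)) must equal the detectable effect from step 3:

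- Two-sided: r = 1 − (0.5/1.06)² / 2 = 0.89.
- One-sided: r = 1 − (0.5/0.93)² / 2 = 0.86.

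Baseline adjustment, which is not planned, has residual variance 1 − r² and would need r of about 0.88 two-sided or 0.84 one-sided. The protocol assumes no correlation at all.

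**The case against.** The strongest defence is that no sum is wrong. The paragraph appeals to recommendations for pilot studies, and the reference list includes papers on planning pilots and on sizing a pilot jointly with a main trial. On that reading 15 is a pilot-size rule, and the 80% and 0.5 belong to a later study. This may well be where 15 comes from. It does not save the text: the paragraph attributes 15 to the listed parameters, no later main trial is mentioned, and the trial is given a superiority hypothesis and between-group tests. The correction is needed on either reading.

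A second objection is that 64 and 26% are the less favourable, two-sided figures, while the alternative in section 2.1 is directional. That is fair as to presentation, and both sets are given above. The one-sided case still needs 51 per group.

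A third is that the plan calls for intention-to-treat analysis with multiple imputation, so all 39 might count. If so, power is at most 33% or 46%, and imputation does not restore information that was never collected.

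Finally, the protocol nowhere says that a non-significant result will be read as lack of efficacy, and effect sizes are already planned. This is true. The risk of misreading comes from the stated 80%, and no confidence intervals are mentioned to offset it.

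**Conclusion.** The sample size statement is wrong as written. The listed inputs give 51 to 64 per group, 3.4 to 4.3 times the stated 15 (51/15 and 64/15). At 15 per group the power for d = 0.5 is 26% two-sided or 38% one-sided. Across completers only to all 39 analysed, and both sidedness options, it runs from 24% to 46%, never near 80%.

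These figures assume a t-test on a single continuous outcome with equal variances, and hold for each primary variable taken alone. Only a pre-post correlation of about 0.86 to 0.89 in a change-score analysis would bring 15 per group to 80% power, and the protocol gives no basis for one. Whether 15 came from a miscalculation or a pilot-size convention cannot be settled from the document, and the conclusion does not depend on it.

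**What to change.** Keep the pilot size and correct what is claimed for it, in the Sample Size Calculation paragraph of section 2.3:

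- Remove the statement that 80% power and d = 0.5 lead to 15 per group.
- Replace it with wording such as: *Fifteen per group is chosen as a pilot size. It gives about 26% power (two-sided 5%) for d = 0.5, and 80% power only for d of about 1.06.* If a one-sided test is intended, say so and use 38% and 0.93.
- State that the aim is to estimate the between-group difference and its SD, reported with a 95% confidence interval, and that a non-significant result will not be read as lack of efficacy. If these estimates are meant to inform a later main trial, say that too; the correction does not depend on it.

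The cost is protocol wording only. No participants are added and the design is unchanged, but the stated power becomes much less favourable.

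### A total of 39 does not absorb the assumed 30% dropout: about 27 would complete, and retaining 15 per group needs 22 per arm (44 in total)

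*Combined protocol and SAP*

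**What the plan says.** All the figures are in section 2.3 of the combined protocol and SAP, under Sample Size Calculation. After listing a two-sample t-test, 5% type I error, 80% power and an effect size of 0.5, the text states that "the recommended total sample size is 15 subjects per group". The next sentence makes the dropout allowance: "Assuming a 30% dropout rate, the total population will be 39 participants". Allocation follows: "After the eligibility process, participants will be randomly assigned to an experimental group (EG) and a control group (CG) using a 1:1 ratio".

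Two other parts of section 2.3 bear on the point. Research Design describes the study this way: "The research design corresponds to a Pilot Randomized Controlled Trial (RCT), with parallel groups and superiority". Statistical Analysis addresses missing data: "Intention-to-treat analysis will be considered using the multiple imputation method for handling missing data and incomplete datasets".

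The inflation formula is not given. Nowhere else do the documents give a different total, a rule for replacing dropouts, an evaluable set or an unequal allocation.

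**The concern.** Raising a total from 30 to 39 for dropout has a purpose only if 30 is the number meant to remain at the end. A dropout rate applies to those who enter, so the number to enter is the target divided by the proportion retained. Multiplying the target by one plus the dropout rate gives too few. Here the result matches the multiplication exactly and falls short of the division.

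If so, the trial is planned to finish below its own target in both arms, even if dropout runs exactly as assumed. A reader would take the sentence to mean that 30% attrition has been covered when it has not. The same slip would also carry into any later recalculation of the sample size.

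**Working it through.** **Inputs** (all from section 2.3, Sample Size Calculation)

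- Target: 15 per group, so 30 in total
- Dropout: 30%, so 0.7 are retained
- Stated total: 39
- Allocation: 1:1; 39 is odd, so the most even split is 20:19
- For the power comparison: t-test for two independent means, d = 0.5, 5% type I error. This paragraph does not state whether the test is one- or two-sided, so both are shown.

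I take 39 as the number randomised. The text calls it the total population and then describes assignment after eligibility, so this is an assumption.

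**Step 1. Reproduce the plan's figure.** Target × (1 + dropout) = 30 × 1.3 = 39.0. The match is exact. That this formula was used is an inference.

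**Step 2. Number needed to retain the target.** Target ÷ (1 − dropout):

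- Per arm: 15/0.7 = 21.4, rounded up to 22; 2 × 22 = 44 in total.
- Pooled: 30/0.7 = 42.9, rounded up to 43. A 22:21 split leaves 21 × 0.7 = 14.7 expected in the smaller arm, so 43 does not quite secure 15 in each.
- Check of 44: 22 × 0.7 = 15.4 per arm.

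**Step 3. Completers expected from 39.**

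- Total: 39 × 0.7 = 27.3, which is 30 − 27.3 = 2.7 short.
- By arm: 20 × 0.7 = 14.0 and 19 × 0.7 = 13.3.

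**Step 4. Dropout that 39 does cover.**

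- For 30 completers in total: (39 − 30)/39 = 9/39 = 23.1%.
- For 15 in the arm of 19: (19 − 15)/19 = 4/19 = 21.1%. At 23.1% dropout that arm expects 19 × 30/39 = 14.6.

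**Step 5. Chance of reaching the target.** Binomial, each participant completing independently with probability 0.7:

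| Randomised | Split | At least 30 complete | Both arms reach 15 |
|---|---|---|---|
| 39 | 20:19 | 22% | 0.416 × 0.282, about 12% |
| 43 | 22:21 | 59% | 0.671 × 0.551, about 37% |
| 44 | 22:22 | 67% | 0.671 × 0.671, about 45% |

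**Step 6. Effect on power from this error alone.** Completers-only t-test, noncentral t with n1 + n2 − 2 degrees of freedom and noncentrality d × √(n1·n2/(n1 + n2)):

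| Completers | Noncentrality | Two-sided 5% | One-sided 5% |
|---|---|---|---|
| 15 and 15 | 0.5 × √7.5 = 1.37 | 26.2% | 37.9% |
| 14 and 13 | 0.5 × √(182/27) = 1.30 | 23.9% | 35.1% |

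The loss is 2.3 points two-sided and 2.8 points one-sided.

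**The case against.** The best defence is about weight and wording, since the arithmetic itself is not in doubt.

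- **The plan never says that 15 must be completers.** True, and it prints no formula. But if 15 were the number to randomise, the total would be 30 and no allowance would be needed. Reading 15 as the number to retain is the only reading that gives the step to 39 a purpose.
- **It is a pilot and the effect is small.** This stands. About 3 completers and 2 to 3 points of power would not change how a pilot is read. The design is also called a superiority trial, however, and a stated allowance should follow from its own inputs.
- **The number being protected is itself unsupported.** This also stands. With d = 0.5, 15 per group gives about 26% power two-sided or 38% one-sided, far from 80%. That is a separate and larger problem, which this error does not cause. If the sample size is derived again, this sentence will be rewritten anyway, and the dropout step should then be done by division.
- **The binomial chances look alarming.** They should be read with care. Even the correctly inflated 44 reaches 15 in both arms only about 45% of the time, because inflation targets the expected number. The main comparison is 27.3 against 30.
- **Multiple imputation keeps dropouts in the analysis.** The plan says only that this will be considered, and imputation does not restore post-intervention values that were never measured.
- **39 might be counted before eligibility losses.** Fewer would then be randomised and the shortfall would be larger.

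**Conclusion.** The concern holds, and the figure is wrong as written: a total of 39, 30% dropout and 15 completers per group are mutually inconsistent. The plan's own assumption yields 27.3 completers where 30 are wanted. Retaining 15 per group requires 44 randomised, 5 more than stated.

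This rests on two assumptions: that 15 per group is the number to retain, and that 39 is the number randomised. It does not depend on how 39 was obtained, since 39 × 0.7 is below 30 in any case. The practical consequence is minor, but the sentence should be corrected.

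**What to change.** Rewrite the dropout sentence under Sample Size Calculation in section 2.3, making clear that 39 is the number randomised. Either of these would be accurate:

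- *With 30% dropout, about 27 of the 39 participants randomised (13 to 14 per group) are expected to complete.*
- *Randomising 39 participants allows for about 23% dropout while retaining 30 in total (about 21% in the smaller arm for 15 per group).*

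The first keeps the 30% assumption. The second changes the dropout that the plan claims to cover, and nothing in the documents supports a rate of 23%, so it suits only a sponsor prepared to defend the lower figure.

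The cost is one sentence. Raising the total to 44 (22 per arm) would also reconcile the figures, at 5 more participants, but the correction does not require it. Neither route addresses the stated 80% power.
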